7.1.6. Summaries of Adverse Events and Deaths

Treatment-emergent AEs will be summarized based on the Safety Analysis Set or Safety Analysis Set for LA regimen, and will be summarized separately for the whole study period analysis and LA regimen period analysis.

For each period analysis, a brief, high-level summary of the number and percentage of participants who experienced at least 1 TEAE in the categories described below will be provided by treatment group and total. All deaths observed in the period will also be included in this summary. The number and percentage of participants who experienced at least 1 TEAE will be provided and summarized by SOC and PT and by PT only for the following AE categories:

- TEAEs
- TEAEs with Grade 3 or higher
- TEAEs with Grade 2 or higher
- TE treatment-related AEs
- TE treatment-related AEs with Grade 3 or higher
- TE treatment-related AEs with Grade 2 or higher
- TE SAEs
- TE treatment-related SAEs
- TEAEs leading to death (by SOC and PT only)
- TEAEs leading to premature discontinuation of study drug
- TEAEs leading to premature discontinuation of study

Multiple events will be counted only once per participant in each summary. For summaries by SOC and PT, AEs will be summarized and listed first in alphabetical order of SOC and then by PT in descending order of total frequency within each SOC. For summaries by PT only, AEs will be summarized and listed by PT in descending order of total pooled cohorts frequency. For summaries by severity grade, the most severe grade will be used for those AEs that occurred more than once in an individual participant during the period.

In addition, data listings will be provided for the following:

- All AEs
- All SAEs
- All Deaths
- All AEs with severity of Grade 3 or higher
- All AEs leading to discontinuation of study drug
- All AEs leading to discontinuation of study

For each listing, whether the event is treatment emergent will be indicated.

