8.6.2. Adverse Events

Clinical and laboratory AEs will be coded using the Medical Dictionary for Regulatory Activities (MedDRA). System organ class (SOC), high-level group term (HLGT), high-level term (HLT), preferred term, and lower-level term (LLT) will be attached to the clinical database.

Events will be summarized on the basis of the date of onset for the event. Any treatment-emergent AEs will be defined as any AE that begins on or after the date of first dose of study drug up to the end of the protocol-defined follow-up period. For participants who discontinue from only the oral LEN, only AEs collected up to 60 days after the last dose date will be considered treatment-emergent.

Summaries (number and percentage of participants) of treatment-emergent AEs (by SOC and preferred term) by treatment group will be provided. Additional summaries will include summaries for AEs by grade, investigator's assessment of relationship to study drug, and effect on study drug dosing.

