8.10. Sample Size

Although the sample size in this study is determined based on practical considerations and past experience with similar types of studies, assuming the 2 treatment groups have a similar virologic suppression rate, a total of 20 participants in the Primary Cohort will provide at least 35% power to show the lower bound of 95% CI for Week 26 virologic response rate (HIV-1 RNA < 50 copies/mL as defined by the FDA-defined snapshot algorithm) is greater than 83%. It was assumed that the virologic response rate at Week 26 was 95% (based on Gilead studies GS-US-380-1844 and GS-US-380-4030), 12% was a clinically tolerable margin for Phase 1b studies, and a one-sided exact test with a significance level 0.025 was used. The sample size and power calculations were made using the statistical software package PASS (Version 14, NCSS, LLC; Kaysville, Utah, USA).

The estimated 95% CI for possible range of VF rate is provided in [Table 8-1](#). For example, with 1 VF event occurrence (5% estimated VF rate), a sample size of 20 participants can provide 95% confidence that the true VF rate is unlikely to be higher than 24.9%.

Table 8-1. Estimated Virologic Failure Rate and its 95% CIs (from the Clopper-Pearson Exact CI) Based on Number of Virologic Failure Event in Each Group or in Total

Sample Size	20				
Number of VF Events	0	1	2	3	4
Estimate of Incidence of VF (%)	0.0	5.0	10.0	15.0	20.0
Lower Bound of 95% CI (%)	0.0	0.1	1.2	3.2	5.7
Upper Bound of 95% CI (%)	16.8	24.9	31.7	37.9	43.7

VF = virologic failure

Software: SAS® Version 9.4. (SAS Institute Inc., Cary, NC, USA)

A total of approximately 20 participants in the Primary Cohort will provide reasonable assessment of safety and the descriptive PK profile throughout the study. A total of up to 20 participants in the optional Pilot Cohort is based on practical considerations.

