3. GENERAL CONSIDERATIONS FOR DATA ANALYSES

Analysis results will be presented using descriptive statistics. For categorical variables, the number and percentage of participants in each category will be presented; for continuous variables, the number of participants (n), mean, standard deviation (SD) or standard error (SE), median, first quartile (Q1), third quartile (Q3), minimum, and maximum will be presented.

By-participant listings will be presented for all participants in the All Randomized Analysis Set and sorted by participant identification (ID) number, visit date, and time (if applicable). Data collected on log forms, such as AEs, will be presented in chronological order within the participant. The treatment group to which participants were randomized will be used in the listings. Age, sex at birth, race, and ethnicity will be included in the listings, as space permits.

There are the following 2 sets of analyses defined for this study. Data included in each analysis are defined as follows:

Long Acting (LA) Regimen Period Analysis

Long-acting (LA) Regimen Period Analysis includes efficacy (ie, HIV-1 RNA and CD4 cell count and percentage) and safety data collected during **Long Acting Regimen Period** from participants randomized and received at least one dose of the complete long acting study drug regimen (ie, SC LEN + GS-5423 and GS-2872) up to ART restart (eg, Week 26). All data collected up to the last exposure date of LA regimen (defined in Section 3.8.1) will be summarized except for data on AEs, death and concomitant medications. For AEs, death and concomitant medications, only data collected prior to the last exposure date of LA regimen will be included. For participants who did not restart ART on or before last study date or have missing ARV restart date, all data will be included.

Data included in this analysis will be used to assess the efficacy and safety data collected during the LA regimen period of the study. Results will be summarized by treatment group and overall.

Whole Study Period Analysis

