7. SAFETY ANALYSES

The primary objective of this study is to evaluate the safety and tolerability of a combination of the bNAbs GS-5423 and GS-2872 in combination with the HIV capsid inhibitor LEN, and the primary endpoint of this study is incidence of treatment-emergent SAEs through Week 26. The second endpoint of this study includes incidence of treatment-emergent AEs through Week 26.

Safety data will be summarized for participants in the Safety Analysis Set for the whole study period analysis and for participants in the Safety Analysis Set for LA regimen period analysis, separately, unless otherwise specified. All collected data will be included in data listings.

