Appendix 5. Programming Specifications

- 1) For categorical efficacy response (eg, Participants with HIV-1 RNA < 50 copies/mL or Participants with HIV-1 RNA \geq 50 copies/mL as determined by US FDA-defined snapshot algorithm, M=F, or M=E Analyses): the proportion difference between two treatment groups and its 95% CIs are calculated based on the an unconditional exact method using 2 inverted 1-sided tests in SAS v9.3 or above.

- 2) The following SAS code will be used to compute cell counts and confidence interval.

```
data example;
input grp trt01a $ outcome $ count ;

datalines;
1      Treat-A      2-Fail      1
1      Treat-A      1-Succ      189
1      Treat-B      2-Fail      4
1      Treat-B      1-Succ      88
run;

proc freq data = example;
table trt01a*outcome /riskdiff(CL=(exact)) alpha=0.05;
weight count; exact RISKDIFF(METHOD=SCORE);
output out=ciexact(keep=_RDIF1_ XL_RDIF1 XU_RDIF1 _RSK11_ _RSK21) riskdiff;
run;
data final(keep=A1 B1 Estimate LowerCL UpperCL ocharc1);
set ciexact;
label Estimate ="Percentage Difference"
LowerCL = "95% Lower Confidence Limit"
UpperCL = "95% Upper Confidence Limit"
A1 = "Percentage of Success in Treat-A"
B1 = "Percentage of Success in Treat-B";
Estimate=100*_RDIF1_;
LowerCL = 100*XL_RDIF1;
UpperCL = 100*XU_RDIF1;
A1 = 100*_RSK11_;
B1 = 100*_RSK21_;
ocharc1 = right(compress(put(Estimate,8.1)) || '%' (' || compress(put(LowerCL,8.1)) || '%
to ' || compress(put(UpperCL,8.1)) || '%'));
run;
```

- 3) The 95% CI for percentage estimate of HIV-1 RNA < 50 copies/mL for each treatment is calculated based on the Clopper-Pearson exact method.
- 4) For figures, if at a visit where n (sample size) for any treatment group \leq 5, data for that treatment group will not be displayed at the visit in figure (except the Kaplan-Meier figure), but all data will be included in the corresponding table summary.
- 5) All screened participants refer to all participants who are screened (ie, with nonmissing screening date) and have a screening number. For summaries the same participant is counted only once. DOB and other demographic information such as sex, race, ethnicity, country, and initials will be used to identify unique screened participants.

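### The sole primary endpoint, treatment-emergent SAEs through Week 26, is planned as number and percentage with no confidence interval, although secondary efficacy proportions get exact 95% intervals

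*SAP*

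**What the plan says.** SAP 7 states that "the primary endpoint of this study is incidence of treatment-emergent SAEs through Week 26". Protocol 8.1.2 names the same single primary endpoint.

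Three places govern how it is summarised, and they agree:

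- SAP 3, for all categorical data: "For categorical variables, the number and percentage of participants in each category will be presented".
- Protocol 8.6.2: "Summaries (number and percentage of participants) of treatment-emergent AEs (by SOC and preferred term) by treatment group will be provided".
- SAP 7.1.6: a high-level table of participants with at least one event in each category, by treatment group and total, and then "The number and percentage of participants who experienced at least 1 TEAE will be provided and summarized by SOC and PT". Treatment-emergent SAEs are one of the listed categories. All SAEs and all deaths are also listed by participant.

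SAP 7.7 records no departure from the protocol's safety analyses. No interval is planned for any adverse event proportion.

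Efficacy is handled differently. Protocol 8.5 calls for exact 95% intervals for the snapshot proportions. SAP Appendix 5 item 3 says: "The 95% CI for percentage estimate of HIV-1 RNA < 50 copies/mL for each treatment is calculated based on the Clopper-Pearson exact method". Item 1 of the same appendix gives exact intervals for differences between groups. Protocol Table 8-1 and SAP Table 1-1 print Clopper-Pearson limits for 0 to 4 virologic failures in 20 participants.

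**The concern.** The primary endpoint is a binomial proportion in a small sample, which is where a percentage on its own says least. The sponsor treats an interval as informative for secondary proportions in the same participants. Its sample-size text interprets one virologic failure in 20 through the upper confidence limit. For SAEs no counterpart exists. There is no target rate, the data review committee has no formal safety stopping rule (Protocol 8.2.1.1), and the safety case for 20 participants is qualitative (Protocol 8.10). An interval would therefore be the only planned statement of which SAE rates the data exclude. At stake is how the primary result reads in the final report, above all in the dose-group columns of about 10 participants each. No test or sample size depends on it.

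**Working it through.** **Inputs.** Primary Cohort of about 20 (Protocol 4.1). Allocation 1:1 (Protocol 5.1.1), so about 20/2 = 10 per group. Method: two-sided 95% Clopper-Pearson (Protocol Table 8-1; SAP Appendix 5 item 3).

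**Formula.** For x events in n, the lower limit is the 2.5% quantile of Beta(x, n − x + 1) and the upper limit is the 97.5% quantile of Beta(x + 1, n − x). With x = 0 the lower limit is 0 and the upper limit is 1 − 0.025^(1/n).

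**The plan's own figures first.** For 0 to 4 events in 20 the formula gives upper limits of 16.84, 24.87, 31.70, 37.89 and 43.66%. Table 8-1 prints 16.8, 24.9, 31.7, 37.9 and 43.7%, so all five agree.

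The power statement also reproduces. The protocol says "a total of 20 participants in the Primary Cohort will provide at least 35% power" and "a one-sided exact test with a significance level 0.025 was used". To put the lower limit above 83%, all 20 must respond: 20/20 has a lower limit of 0.025^(1/20) = 83.2%, and 19/20 has only 75.1%. Power at a 95% response rate is 0.95^20 = 35.8%. The 83.2% limit for 20/20 responders is the complement of the 16.8% limit for 0/20 events, so the sample-size argument already rests on the quantity that is missing for SAEs.

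**Applied to the primary endpoint.**

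| Participants with an SAE | Total, n = 20 | One group, n = 10 |
|---|---|---|
| 0 | 0 to 16.8% | 0 to 30.8% |
| 1 | 0.1 to 24.9% | 0.3 to 44.5% |
| 2 | 1.2 to 31.7% | 2.5 to 55.6% |

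**Chance of seeing no SAE.** The documents give no expected SAE rate, so the true rates below are assumptions, shown as a range. The formula is (1 − p)^n.

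| Assumed true rate | n = 20 | n = 10 |
|---|---|---|
| 5% | 35.8% | 59.9% |
| 10% | 12.2% | 34.9% |
| 16.8% | 2.5% | 15.9% |

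**Sensitivity of the 0-event limit.**

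- If the actual total is 18 to 22, the two-sided upper limit runs from 18.5% down to 15.4%.
- A one-sided 95% bound for 0/20 would be 1 − 0.05^(1/20) = 13.9%.
- If the Pilot Cohort filled and 40 were pooled, 0/40 would give 8.8%. Protocol 3.1 assesses the study endpoints in the Primary Cohort only, so this figure does not describe the primary endpoint.

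**The case against.** The strongest reply is that this is a descriptive Phase 1b study whose safety reporting is internally consistent. Efficacy has intervals because the sample size is discussed against a target, a lower limit above 83%; safety has no target. Nothing is lost either: anyone with the count and denominator can compute the limits, and those for 20 participants are already printed under the virologic failure label. With so few participants, individual SAEs can be judged from the listings.

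Much of this stands and lowers the weight of the point. It does not remove it. A confidence interval is an estimate and needs no target, hypothesis or multiplicity adjustment. SAP 8.3.2 gives 95% intervals for descriptive pharmacokinetic parameters on the same footing. The printed table covers n = 20 only, not the groups of about 10.

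Three stronger readings are tempting and should not be adopted:

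- A reader might infer that the plan would take zero SAEs as proof of safety. Neither document says so. The stated objective is to evaluate safety and tolerability, and it names no rate to be excluded.
- A reader might infer that 0 or 1 SAE is the expected result. No source supports this. The probability of 0 or 1 in 20 is about 94% at a true rate of 2%, 74% at 5% and 39% at 10%. The point does not depend on it, because the limits are wide at any count.
- A reader might infer that SAEs appear only as a bare count. SAP 7.1.6 also plans tables by system organ class and preferred term, treatment-related SAEs, two analysis periods, and listings.

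Timing also limits the gain. SAP 2.2 records that the Week 26 primary analysis has been conducted, and this SAP covers the final analysis (SAP 1 and 2.4).

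**Conclusion.** The point holds as a low-cost reporting improvement. The primary endpoint has no planned interval in either document, while secondary efficacy proportions do, and the omitted uncertainty is large: an upper limit of 16.8% with no events in 20, and 30.8% with none in a group of 10. These figures assume exactly 20 and 10 participants and the two-sided 95% convention that the documents use for virologic failure. The omission does not invalidate the trial or bias any estimate.

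**What to change.** In the high-level adverse event summary of SAP 7.1.6, add the proportion of Primary Cohort participants with at least one treatment-emergent SAE with onset through Week 26. Use the Safety Analysis Set (any dose of study drug), with Clopper-Pearson 95% limits by treatment group and in total, following Appendix 5 item 3. Record the addition in SAP 7.7.

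The period and population need care, because the long-acting regimen period is not the same quantity. It ends at ART restart, takes in all data where ART was not restarted or the restart date is missing (SAP 3 and 3.8.1), and uses participants who received the complete regimen (SAP 3.1.4). If that period is used instead, the table should say that it ends at ART restart and uses the complete-regimen set.

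The cost is a sentence in each of two SAP sections and three intervals in one table. No new data, method or sample size is needed. The drawback is a safety result that looks less precise. The change reaches the final clinical study report only.

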7.1.7. Additional Analysis of Adverse Events

7.1.7.1. Study Drug Related Injection Site Reactions and Infusion Related Reactions

Additional analysis of AEs will be performed for injection site reaction (ISR) as defined by high level term (HLT) of "Injection site reactions", and infusion related reaction (IRR) as defined per eCRF (ie, AE with "Yes" answer to "Is this part of an infusion-related reaction?" in AE CRF), respectively. The following summaries will be provided for LA regimen period analysis only.

- Number of participants received any injection or infusion
- Number and percentage of participants with study drug related ISRs or IRRs
- Number and percentage of participants with study drug related ISRs or IRRs by grade
- Number and percentage of participants with study drug related ISRs or IRRs by PT

The denominator for the percentage calculation will be based on the number of participants received at least one injection or infusion in Safety Analysis Set .

Duration of the ISR will also be calculated and summarized. Duration of a given ISR event is defined as the ISR stop date minus the ISR onset date plus 1 day. For ISRs with ongoing stop date, stop date will be imputed as last study date or database finalization date, whichever is the earliest. Duration of ISR events in days will be summarized by PT and overall using descriptive statistics. Duration of a given IRR event is defined as the IRR stop date minus the IRR onset date plus 1 day, and duration of IRR will be listed also.

By-participant listings for ISRs or IRRs will be provided.

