7.7. Toxicity Management

All clinical and clinically significant laboratory toxicities will be managed according to uniform guidelines detailed in [Appendix 3](#), and as outlined below:

Grade 3 or 4 clinically significant laboratory abnormalities should be confirmed by repeat testing as soon as possible, and preferably within 3 calendar days after receipt of the original test results.

Treatment-emergent toxicities will be noted by the investigator and brought to the attention of the Gilead medical monitor, and the appropriate course of action will be discussed and decided. Whether or not considered treatment-related, all participants experiencing AEs must be monitored periodically until symptoms subside, any abnormal laboratory values have resolved or returned to baseline levels or they are considered irreversible, or until there is a satisfactory explanation for the changes observed.

Any questions regarding toxicity management should be directed to the Gilead medical monitor.

All clinical sequelae in relation to these SSRs will be reported as AEs or SAEs at the same time using the AE eCRF and/or the SAE report form. Details of the symptoms and signs, clinical management, and outcome will be reported, when available.

7.7.1. Management of Adverse Events of Injection Site Reactions of Grade 3 or Higher or Persisting for More than 26 Weeks

In clinical studies of SC LEN, Grade 3 or higher AEs of injections site reactions (ISRs) were uncommon. Some participants experienced AEs of injection site nodule and induration, which decreased in size over 6 months or longer. For AEs of ISRs related to SC LEN administered from a borosilicate vial that are Grade 3 or higher or persisting for more than 26 weeks, particularly nodule and/or induration, the investigator must contact the Medical Monitor and obtain consultation with an independent dermatologist to evaluate the ISRs.

If clinically indicated as determined by the independent dermatologist, a biopsy of the SC injection site may be performed. The histopathology should be reviewed by an independent dermatopathologist; if a dermatopathologist is not locally available, the histopathology may be reviewed by an otherwise medically qualified person.

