7.1.7.2. Study Drug Related Injection Site Induration and Nodules

Percentage of ongoing and resolved study drug related “Injection Site Induration” (one of preferred terms of ISR) will be summarized at both participant-level and event-level.

For the participant-level summary, if a participant had more than one injection site indurations, the participant will be counted in the “Ongoing” category unless all study drug related injection site induration events have been resolved.

For the event-level summary, duration of the resolved events will be summarized using descriptive statistics.

Study drug related “Injection Site Nodules” (another preferred term of ISR) will be summarized in the same manner as defined for study drug related injection site induration.

A by-participant listing for study drug related injection site induration and nodules and the corresponding duration will be provided.

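### ISR duration summaries are biased short because ongoing events are not treated as censored; persistence is only partly tabulated, and never against the protocol's 26-week mark

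*SAP*

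**What the plan says.** SAP 7.1.7.1 covers all study-drug-related ISRs. Its definition is: "Duration of a given ISR event is defined as the ISR stop date minus the ISR onset date plus 1 day". For events still open it adds: "For ISRs with ongoing stop date, stop date will be imputed as last study date or database finalization date, whichever is the earliest". The output is: "Duration of ISR events in days will be summarized by PT and overall using descriptive statistics". No censoring method is named. The final analysis follows completion or discontinuation by all participants (SAP 2.4), so the last study date will normally be the earlier of the two dates. SAP 3.8.1 defines it as the latest clinic or laboratory visit, follow-up visits included, which is about Day 364 for a completer.

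SAP 7.1.7.2 deals separately with induration. The percentages ongoing and resolved "will be summarized at both participant-level and event-level", and a participant counts as ongoing unless every induration event has resolved. On duration it says: "For the event-level summary, duration of the resolved events will be summarized using descriptive statistics". Nodules "will be summarized in the same manner as defined for study drug related injection site induration". A by-participant listing with durations is also planned.

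Protocol 7.7.1 describes earlier experience with subcutaneous lenacapavir: "Some participants experienced AEs of injection site nodule and induration, which decreased in size over 6 months or longer". It has a specific provision for ISRs that last more than 26 weeks.

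**The concern.** The duration of an event that is still open when observation stops is right-censored: all that is known is that it exceeds the time observed. One SAP section enters that lower bound as a completed duration, and the other drops the event. Both move the summary towards shorter durations, and the shift grows with the share of events still open.

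The protocol makes open events plausible here. It reports nodules and indurations shrinking over six months or more, while scheduled follow-up ends at Week 52. Induration was also common in the earlier healthy-volunteer study (Protocol 1.2.4.1): 47 of 60 participants overall, and 10 of 10 in the cohort given 927 mg as two 1.5 mL injections, which is the presentation used in this trial. Those counts are blinded and include placebo recipients.

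Safety and tolerability are the primary objective, and how long local reactions last is part of that. Because induration and nodule are themselves ISR preferred terms, the same events will also appear with two different duration summaries, neither of which handles censoring.

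**Working it through.** The plan states no figure for ISR duration, so there is none to reproduce. The check is of the direction of each rule, and then of size under stated assumptions.

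**Direction.** Let T be the true duration and C the time from onset to the end of observation. SAP 7.1.7.1 summarises min(T, C), which is never greater than T. SAP 7.1.7.2 summarises T among events with T ≤ C, which is stochastically shorter than T. Neither can err upwards.

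**Inputs.** C = 364 days, taking onset near Day 1 and follow-up to Week 52 (Protocol 3.3). The distribution of T and the rate of early exit are not in the documents, so both are assumed.

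**Formulas for exponential T with median m:**
- Rate λ = ln 2 / m; true mean = 1/λ.
- Share resolved F = 1 − exp(−λC).
- Mean under imputation = F/λ.
- Mean of resolved events = (F/λ − C(1 − F)) / F.
- Median of resolved events = −ln(1 − F/2) / λ.

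For m = 182: 1/λ = 262.6 and F = 0.75. The imputed mean is 0.75 × 262.6 = 197. The resolved-only mean is (197 − 91)/0.75 = 141. The resolved-only median is −ln(0.625) × 262.6 = 123.

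For m = 364: 1/λ = 525 and F = 0.50. The imputed mean is 0.50 × 525 = 263. The resolved-only mean is (263 − 182)/0.50, or 161 before rounding. The resolved-only median is −ln(0.75) × 525 = 151.

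| Assumed true median (days) | Ongoing | Mean: true / imputed / resolved-only | Median: true / imputed / resolved-only |
|---|---|---|---|
| 90 | 6% | 130 / 122 / 106 | 90 / 90 / 82 |
| 182 | 25% | 263 / 197 / 141 | 182 / 182 / 123 |
| 364 | 50% | 525 / 263 / 161 | 364 / 364 / 151 |

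**The median under imputation.** With complete follow-up and fewer than half the events open, the imputed median is correct. In the last row it agrees only because the true median was set equal to C. With a true median of 500 days it would be held at 364. With true median 182 days and an assumed 10% to 20% leaving early, simulation puts the imputed median at 171 to 161 days.

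**Share lasting beyond 26 weeks.** With true median 182 days and 10% leaving early, the true share is about 50%. The imputed durations give 48% and the resolved-only durations 32%.

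**Other shapes.** Weibull with shape 1.5 and median 60 days gives a mean of 69 days under all three approaches, so the bias is negligible. Weibull with shape 0.7 and median 364 days gives an imputed mean of 246 against 775 days. A halving is therefore an illustration and not a ceiling.

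**The case against.** The strongest answer is that persistence is not hidden. SAP 7.1.7.2 tabulates ongoing against resolved for the two terms that matter most, with a participant rule that leans towards persistence, and it lists the durations. A reader might infer that persistence as such is understated, or that nodule and induration durations rest on resolved events throughout the SAP. The documents support neither. The ongoing percentages are reported, and the by-term summary in 7.1.7.1 includes the open events that 7.1.7.2 leaves out.

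It is also fair to say that the imputation rule need not move the median and barely disturbs a 26-week classification (48% against 50% above). It uses the longest observation available, because it runs to the last study date and not to ART restart. The long-duration scenarios are assumed: the protocol says only that some participants had reactions lasting six months or more. True means beyond 52 weeks could not be recovered by Kaplan-Meier without extrapolation either. With about 20 participants per cohort and two injections each, estimates by preferred term will be sparse and events will cluster within participants.

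These points limit the concern but do not remove it. The ongoing category has no time axis: someone who leaves at Week 8 with induration counts the same as someone still affected at Week 52. ISR terms other than induration and nodule have no ongoing/resolved table, so real and imputed stop dates are mixed in one summary with only listings to separate them. The 26-week classification survives imputation fairly well, but no table reports it.

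**Conclusion.** The point holds as a bias in the duration summaries, not as a failure to report persistence. The direction is certain whenever events are ongoing: 7.1.7.1 lowers the mean, the maximum and possibly the third quartile, and the median only with early exit or when half or more of the events are open. The resolved-only summary in 7.1.7.2 lowers every statistic.

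The size cannot be derived from the documents. It depends on the assumed duration distribution, on onset near Day 1 and on how many participants leave early. In the cases worked here it ranges from nothing visible to a halved mean or worse. A reader might take the larger figures as a forecast, but the documents give no duration distribution that would support that.

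These are descriptive safety tables. The primary endpoint, incidence of treatment-emergent SAEs through Week 26, is untouched.

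**What to change.** Summarise time to resolution of ISRs, including induration and nodules, by Kaplan-Meier with ongoing events censored at the last study date. Report:
- the median, or 'not reached', and quartiles where estimable;
- the proportion unresolved at 26 weeks after onset and at the latest time the data support;
- the number ongoing beside each duration, for every preferred term.

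Keep the existing ongoing/resolved tables and the listings. If the current summaries are retained, label the 7.1.7.2 durations as resolved-only and the imputed durations in 7.1.7.1 as lower bounds.

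The change needs SAP wording and a standard procedure on data already collected. Its costs are sparse estimates by preferred term, several events per participant (so intervals that treat events as independent should be avoided or caveated), and longer reported durations. The censoring also assumes that leaving the study is unrelated to how long a reaction lasts, which should be stated with the table.
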